19.4 Safety Monitoring

Safety Evaluation: A previous Phase I study utilized the same dosing strength (at a different dosing schedule: 5 days versus the proposed 3 days), but only gave one cycle; whereas the current study purposes 3 consecutive weeks of 3-day treatments. As such, a continuous toxicity monitoring plan will be implemented to quickly identify the emergence of any new AEs or SAEs.

Subject safety will be monitored continuously using Bayesian methods with the following decision rule: if the posterior probability is .80 or greater than 33% or more of treated subjects experience a treatment related serious adverse event (SAE), then the study will be suspended pending review. This posterior probability will be calculated from the study's accumulating data and a weakly informative prior distribution. If π denotes a random variable representing the proportion of subjects who will experience a treatment related SAE, we assume π has a beta distribution with parameters $a = 1$ and $b = 2$.

Selected values of the posterior distribution $PP(\pi \geq .33 | \text{SAEs and prior})$ are shown in the table below. Also shown are the binomial probabilities of suspending the study for observed count of SAE's.

Table X Number of Subjects Observed to Have Treatment-Related SAEs and Corresponding Posterior and Binomial Probabilities Needed to Suspend the Study

Subjects	Treatment-Related SAEs	$PP(\pi > 33\%)^*$	$Pr(X \geq r p = .33)$
2	2	.892	.109
3	3	.956	.036
4	3	.903	.108
5	3	.832	.205
6	4	.915	.097
7	4	.860	.168
8	5	.927	.085
9	5	.883	.140
10	5	.829	.206

PROTOCOL TITLE: Phase 2A Study Evaluating a Chemokine-Modulatory Regimen in Patients with Colorectal Cancer Metastatic to the Liver

11	6	.901	.117
12	6	.857	.171
13	6	.805	.233
14	7	.880	.143
15	7	.836	.195

* π is the SAE rate. The minimum acceptable upper bound of a treatment-related SAE is 33%. PP($\pi > 33\%$) is the posterior probability that the SAE rate exceeds this 33% upper bound. This posterior probability of an SAE is calculated from the prior distribution, the number of subjects treated and the observed number of treatment-related SAEs.

It is anticipated that 15 patients will be enrolled to this study. The table above presents the minimum number of subjects experiencing treatment-related SAEs (i.e., those SAEs judged to be possibly, probably, or definitely related to the study regimen) that would dictate suspension of the trial in accordance with the stopping rule. Using these assumptions the trial will be suspended if:

- 2 subjects experience treatment related SAE among the first 2 subjects enrolled
- 3 subjects experience treatment related SAE among 3 – 5 subjects or,
- 4 subjects experience treatment related SAE among 6 – 7 subjects or,
- 5 subjects experience treatment related SAE among 8 – 10 subjects or,
- 6 subjects experience treatment related SAE among 11 – 12 subjects,
- 7 subjects experience treatment related SAE among 13 – 15 subjects.
- Any death not clearly due to the underlying disease or extraneous causes

At the completion of the study, all AEs will be summarized by weekly treatments and grade using frequencies and relative frequencies.

Treatment Related SAEs for Safety Monitoring

Treatment Related SAEs will be defined as the following events that occur during the period of Day 1 through the End of Treatment visit:

- \geq Grade 3 treatment-related non-hematologic toxicities, except:
 - The following grade \geq 3 toxicities (lasting <7 days)
Flu-like symptoms/constitutional symptoms (i.e., fever, chills, arthralgias, myalgias)
Depression, anxiety, restlessness, or insomnia
GI symptoms (i.e., nausea, diarrhea)
AST/ALT (unless accompanied by Grade 2 increased bilirubin)
 - Please note, if the above grade 3 toxicities last ≥ 7 days, they will be defined as a DLT
- \geq Grade 4 treatment related non-hematologic toxicity
- Hy's law criteria:

PROTOCOL TITLE: Phase 2A Study Evaluating a Chemokine-Modulatory Regimen in Patients with Colorectal Cancer Metastatic to the Liver

- An elevated alanine transaminase (ALT) or aspartate transaminase (AST) lab value that is greater than or equal to three times (3X) the upper limit of normal (ULN) and
- An elevated total bilirubin lab value that is greater than or equal to two times (2X) ULN and, at the same time, an alkaline phosphatase (ALP) lab value that is less than 2X ULN,
- As a result of within-protocol-specific testing or, unscheduled testing

Safety Review and Study Suspension

The Roswell Park Data Safety and Monitoring Committee (DSMC) will assess the progress of the study, the safety data, and critical efficacy endpoints. The DSMC will review the study annually and will make recommendations that include but not limited to; (a) continuation of the study, (b) modifications to the design (c) or termination of the study.

Additionally, should the study be suspended due to safety; members of the research team, study statistician, and DSMC will meet to discuss safety concerns and possible adjustments to the study or study closure.

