10.2.3 Toxicity Management

The toxicity of high dose interferon (20million units/m²/d) has been established by Kirkwood et al in a number of trials. Most notable was the E1684 trial [68] where HDI (20 million units/m²/d) was administered daily for 5 days x 4weeks. In that trial (n=143), grade 3 toxicities were 67%, grade 4 toxicities were 9% (mainly constitutional and neurologic), and there were 2 treatment related mortalities (grade 5) due to hepatotoxicity. The proportion of Grade 3 and 4 toxicities in that trial were 48.2% for constitutional toxicities (defined as ‘worst grade of any constitutional toxicity, including fever, chills, flu-like symptoms, fatigue, malaise, and diaphoresis), and 66% for non-constitutional toxicities (23.8% for myelosuppression, 13.9% for hepatotoxicity, 28% for neurological toxicity).

While the combination of HDI and rintatolimod may lead to synergistic additive side effects, we will monitor subject toxicities for unexpected increases in constitutional symptoms, myelosuppression, hepatotoxicity, and neurological toxicity. Moreover, the presence of celecoxib may improve the side effect profile. Rather than a separate phase of the study to characterize safety, we will use continual Bayesian monitoring of SAEs with a stopping rule that permits suspension of the trial by the investigator for review by the Data Safety and Monitoring Committee (DSMC). We will focus on monitoring for grade 3 or greater treatment related hematologic toxicities, and grade 4 or greater treatment related non-hematologic toxicities. A non-informative prior distribution of SAEs will be utilized to develop the safety stopping rules (details in Section 19.4).

- **Gastrointestinal Toxicity:**

- Nausea and/or vomiting should be controlled with adequate antiemetic therapy. Prophylactic antiemetic therapy can be used at the discretion of the investigator/sub-investigator. Subjects are encouraged to take plenty of oral fluids.
- Diarrhea should be managed with appropriate antidiarrheal therapy. Subjects should be encouraged to take plenty of oral fluids. If symptoms do not decrease to grade 1 or less with adequate antidiarrheal therapy, all protocol drugs should be held until resolved to < grade 1.

- **Pain**

- For fever or mild local pain, acetaminophen will be utilized at the discretion of the investigator/sub-investigator or designee.

- **Hypersensitivity Reactions**

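### Table X gives single-look binomial tails as the probabilities of suspending the study; under the continuous rule the chance at a 33% event rate reaches about .38 (.37 with the bulleted boundary) by 15 subjects, above every printed value

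*Combined protocol and SAP*

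**What the plan says.** Section 19.4 states that "Subject safety will be monitored continuously using Bayesian methods with the following decision rule". The study is suspended pending review once the posterior probability that the treatment-related SAE rate is 33% or more reaches .80. The prior is Beta(1,2), which the section calls weakly informative.

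Table X lists, for 2 to 15 subjects, the event count that triggers suspension, the posterior at that count, and a last column headed Pr(X >= r | p = .33). The text introduces that column as follows: "Also shown are the binomial probabilities of suspending the study for observed count". The footnote gives the reference rate: "The minimum acceptable upper bound of a treatment-related SAE is 33" per cent.

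A bulleted list after the table restates the boundary in ranges of subjects and adds a separate trigger for certain deaths. Table X requires 6 events at 13 subjects; the bullet covering 13 to 15 subjects requires 7.

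Section 10.2.3 describes the same rule and refers to 19.4 for details, but characterises the prior differently: "A non-informative prior distribution of SAEs will be utilized to develop the safety stopping rules".

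**The concern.** A rule checked after every subject suspends the study if its boundary is crossed at any subject count reached so far. The probability of having suspended therefore accumulates and can never fall. A tail computed at one sample size ignores crossings at smaller sizes where the count later drops back below the boundary.

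The printed column falls five times: from .109 to .036, .205 to .097, .168 to .085, .206 to .117 and .233 to .143. At 3 subjects it shows .036, although two events in the first two subjects would already have suspended the study with probability .109. The introductory sentence therefore assigns the column a meaning its numbers cannot have.

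This matters because 10.2.3 uses the monitoring in place of a separate safety phase, and the column is the only information given on how the rule behaves. A reader who trusts the sentence would underestimate how often the trial pauses at the 33% limit. The column also says nothing about higher or lower true rates.

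**Working it through.** **Inputs**, all from 19.4: prior Beta(1,2); reference rate .33; posterior threshold .80; continuous checking; the Table X boundary and the bulleted boundary; a maximum of 15 subjects ("It is anticipated that 15 patients will be enrolled to this study").

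**Step 1: reproduce the printed figures.** With r events in n subjects the posterior is Beta(1 + r, 2 + n − r), and the tail is the binomial Pr(X >= r | n, .33). At n = 15, r = 7 these give .8358 and .1951, against the printed .836 and .195. All 14 rows of both columns reproduce to three decimals. Each Table X boundary is the smallest r whose posterior is at least .80. With 1 event in 1 subject the posterior is .745, so suspension cannot occur before the second subject.

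**Step 2: first rows by hand, p = .33.**

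- n = 2 (boundary 2): .33² = .1089.
- n = 3 (boundary 3): three of three requires two of the first two, which has already suspended. Nothing is added; the cumulative value stays .1089.
- n = 4 (boundary 3): one event in the first two, then events in subjects 3 and 4. This adds (2 × .33 × .67) × .33² = .4422 × .1089 = .0482, giving .1571.
- n = 5 (boundary 3): not yet suspended, exactly 2 events after four subjects, then an event. The chance of 2 events after four without suspension is .4422² + .67² × .33² = .1955 + .0489 = .2444. This adds .2444 × .33 = .0807, giving .2377. The printed value is .205.

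**Step 3: all rows.** The same forward recursion, removing probability at the boundary after each subject, gives:

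| Subjects | Table X boundary | Printed tail | Cumulative suspension probability |
|---|---|---|---|
| 2 | 2 | .109 | .109 |
| 3 | 3 | .036 | .109 |
| 4 | 3 | .108 | .157 |
| 5 | 3 | .205 | .238 |
| 7 | 4 | .168 | .270 |
| 10 | 5 | .206 | .323 |
| 12 | 6 | .171 | .339 |
| 13 | 6 | .233 | .368 |
| 15 | 7 | .195 | .381 |

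A simulation of 2,000,000 trials also gave .381 at 15 subjects. With the bulleted boundary (7 at 13 subjects) the values are .339 at 13, .348 at 14 and .368 at 15. The ratio to the printed figure at 15 is .381 / .195 = 1.95, or .368 / .195 = 1.89.

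**Step 4: other true rates, by 15 subjects.**

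| True rate | Table X boundary | Bulleted boundary |
|---|---|---|
| 10% | .017 | .017 |
| 20% | .105 | .101 |
| 25% | .190 | .183 |
| 33% | .381 | .368 |
| 50% | .814 | .802 |

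**Step 5: looks less often than every subject.** With the Table X boundary at p = .33, checking every 5 subjects gives .332 and every 3 subjects .271. Both still exceed the largest printed value, .233.

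**The case against.** The strongest reply is that nothing in the table is miscalculated. The header states exactly what is shown, the table title calls the values binomial probabilities, and the introductory sentence ties them to an observed count. The visible falls in the column should warn a careful reader that it is not cumulative. No decision depends on it: the operative rule is the posterior threshold, expressed as counts. Crossing leads to suspension pending review, not termination, and more frequent pausing at the protocol's own upper limit errs towards caution.

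Most of this stands and limits the point. A reader might infer that the Table X arithmetic is wrong; it reproduces in full. A reader might infer that the plan offers .195 as a whole-study error rate; it makes no such explicit claim, and .195 is one row. A reader might also infer from 10.2.3 that a uniform prior was intended and that the rule would then behave differently. The documents do not support that: 10.2.3 defers to 19.4, 19.4 specifies Beta(1,2), and Table X reproduces under it. The conflict is one of description.

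The reply does not rescue the introductory sentence. It calls these figures probabilities of suspending the study in a section that specifies continuous monitoring, and no other figure for that quantity is given.

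**Conclusion.** The description of the last column is wrong as written. At a true rate of 33% the rule suspends the study by 15 subjects with probability .381 under Table X or .368 under the bullets. That is nearly twice the .195 printed for 15 subjects and above every entry in the column. The cumulative figure already exceeds the column maximum at 5 subjects (.238 against .233).

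This rests on independent subjects with a common event rate, a check after each subject, and the SAE-count rule alone. The death trigger could only raise the probability.

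It would be too strong to conclude that the posterior threshold is unsound or that participants are less protected: the counts in Table X follow from the stated threshold and prior. Nor can the boundary be called settled, because Table X and the bullets disagree at 13 subjects. Six events there give a posterior of .805, which is why Table X lists 6. This review does not choose between the two; the cumulative figures depend modestly on which is adopted.

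**What to change.** 1. Reconcile the boundary at 13 subjects between Table X (6 events) and the bulleted list (7 events), so that one boundary applies throughout 19.4.
2. Describe the last column of Table X as a single-look binomial tail at each row's sample size, and amend the introductory sentence to match.
3. Add the cumulative suspension probabilities for the reconciled boundary at several true rates, such as the five tabulated in the working, and state that they assume a check after each subject and exclude the death trigger.
4. Reconcile the non-informative prior of 10.2.3 with the weakly informative Beta(1,2) prior of 19.4 that generated Table X.

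The cost is a short added table and a few sentences, with no new data. The one drawback is that the stated probability of suspension at a 33% rate becomes less favourable.

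### The Section 19.4 suspension rule counts subjects still inside the event window as known non-events, so a pending subject can pre-empt a suspension at the last n of a step; the effect at planned accrual is modest

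*Combined protocol and SAP*

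**What the plan says.** Section 19.4 states: "Subject safety will be monitored continuously using Bayesian methods". The prior is Beta(1, 2), and the study is suspended pending review when the posterior probability of an SAE rate above 33% is .80 or more.

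The denominator is described in two ways. The Table X footnote bases the posterior on "the number of subjects treated and the observed number of treatment-related SAEs". The suspension list starts with "2 subjects experience treatment related SAE among the first 2 subjects enrolled" and continues with "3 subjects experience treatment related SAE among 3 – 5 subjects or" and similar items that refer only to subjects.

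The events that count are "the following events that occur during the period of Day 1 through the End of Treatment visit". Section 11.1.5 places that visit at Day 29 ± 10.

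I found no text that requires a completed window before a subject enters n, gives partial weight to partial follow-up, or staggers entry. Section 7 plans 15 participants over about 48 months.

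**The concern.** Section 19.4 defines π as the proportion of subjects who will eventually have a treatment-related SAE. The update to Beta(1 + r, 2 + n − r) is correct when all n outcomes are known. A subject in the first days of treatment has an unknown outcome, yet is counted in full as event-free. The posterior is then too low whenever someone is still in the window.

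This matters because Section 10.2.3 uses this monitoring in place of a separate safety phase. Section 19.4 justifies it by the step from one cycle in the earlier phase I study to three consecutive weeks here, so events after repeated dosing are the ones it needs to catch. Several grade 3 or higher toxicities count only once they have lasted 7 days or more, which leaves time for another subject to start before the event is confirmed. If suspension is delayed or missed, more subjects are dosed after the informative data have reached the limit.

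**Working it through.** **Inputs.** From 19.4: prior Beta(1, 2), rate .33, cut-off .80, and the Table X limits. From 11.1.5: window end at Day 29 ± 10. From Section 7: 15 subjects in 48 months.

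**Reproducing Table X.** With r events in n subjects, the posterior is P(π > .33) under Beta(1 + r, 2 + n − r). For 2/2 this is Beta(3, 2), which gives .892 as printed. All 14 rows match to three decimals in both the posterior and the binomial column.

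**Adding one pending subject.** A just-dosed subject with no event changes (n, r) to (n + 1, r), so the second parameter rises by 1:

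| Limit | Posterior | With one pending subject | Posterior |
|---|---|---|---|
| 2/2 | .892 | 2/3 | .795 |
| 3/5 | .832 | 3/6 | .748 |
| 4/7 | .860 | 4/8 | .794 |
| 5/10 | .829 | 5/11 | .767 |
| 6/13 (Table X only) | .805 | 6/14 | .747 |

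Each falls below .80. These are the last n of each step. At other n one pending subject is not enough; for example, 3/4 at .903 becomes 3/5 at .832. The last row is a limit only in Table X, because the list asks for 7 among 13–15. The two texts conflict there and must be reconciled.

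**Weighting by observed follow-up.** Suppose the pending subject adds w to the second parameter, where w is the fraction of the window observed without an event. At w = 0 the posterior stays at its limit value. It drops below .80 only when w reaches about .95 (2/2), .39 (3/5), .91 (4/7), .48 (5/10) or .09 (6/13).

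**How often windows overlap.** The mean gap is 48 × 30.44 / 15 = 97.4 days. With random (Poisson) arrivals, the chance that the next subject starts within d days is 1 − exp(−d / 97.4): .26 for 29 days, and .18 to .33 for 19 to 39 days.

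**Effect on suspension.** Simulation of 15 subjects, assuming a 97-day mean gap, a 29-day window and events uniform over the window. The treated count is compared with a count of subjects who have had an event or completed the window:

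| True SAE rate | Ever suspended, treated count | Ever suspended, event-or-completed count | Never suspended under the treated count, among trials the other count suspends |
|---|---|---|---|
| 33% | about .38 | about .40 | about 5% |
| 50% | about .81 | about .82 | about 1.5% |

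Later and never together make up about 15–18% of the trials that the event-or-completed count suspends. With the weighted count, suspension at a true 33% rate is about .39.

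**The case against.** A reader might infer that one newly dosed subject can cancel a suspension already required. The documents do not support that. Monitoring is continuous, so once 2/2 is observed the study is suspended and a later subject cannot undo it. The weakness is pre-emption: the pending subject has to be counted before the deciding SAE is recorded.

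The first list item can also be read by enrolment order. If subject 3 has just started and subject 2 then has a qualifying SAE, both of the first two enrolled have had events and the list still calls for suspension. On that reading the dilution from 2/2 to 2/3 arises only through the footnote's posterior. This is a fair point, and it shows that the texts disagree. It does not help at the later steps, which carry no such wording.

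The comparison rule in the simulation is itself not neutral. It admits events at once and non-events only when the window closes, so it leans towards suspension. In one run about 14% (true rate 33%) or 10% (true rate 50%) of its suspensions came when the complete outcomes of subjects already dosed would not have met Table X. Part of the delay attributed to the treated count is therefore the comparator acting early.

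There are also safeguards that do not depend on n: the trigger for certain deaths in 19.4, individual discontinuation for grade 4 related toxicity in 10.2, annual DSMC review, and the early-phase trial meetings in Section 20. They limit the consequences but do not correct the posterior.

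**Conclusion.** The point holds in a limited form. As written, 19.4 scores subjects with unknown outcomes as non-events. This can pre-empt suspension at the last n of a step: 2, 5, 7 and 10, and also 13 by Table X. The posterior results are exact under the plan's own model.

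The practical effect at 15 subjects in 48 months is modest: about two percentage points in the chance of ever suspending at a true 33% rate, and about one at 50%. The larger figure of 15–18% combines delayed with missed suspensions and is measured against a rule that leans early. These sizes rest on random arrivals, a 29-day window and uniform event times, none of which the plan states. The effect would grow if accrual bunched, but the documents give no basis for assuming a faster pace. It would be wrong to infer that the rule fails when the regimen is clearly too toxic, since at a true 50% rate the trial is suspended in about four of five cases under either count.

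**What to change.** Use one defined denominator in the decision rule, the suspension list and the Table X footnote, replacing the mix of treated and enrolled. Two versions would work:

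- Count subjects who have had a qualifying event or have completed the window. This is simple and leaves the Table X calculations unchanged, but it leans towards suspension because events enter before non-events.
- Count each event-free subject still in the window by the fraction of the window observed. This avoids most of that lean but needs the posterior computed at each look, because n is no longer a whole number.

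In either case, state that the posterior is re-evaluated at each qualifying event and each window closure. While editing, reconcile Table X with the list at 13 subjects.

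The cost is a protocol wording change and slightly more frequent and earlier suspensions for review: at a true 33% rate, about .39 (weighted) or .40 (event or completed) against about .38 now. Because suspension leads to a review and not directly to closure, that is a small price.

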10.2 Dose Modification

The following dose modification rules will be used with respect to potential toxicity. Toxicity will be assessed according to the NCI Common Terminology Criteria for Adverse Events Version 5.0 (CTCAE v5.0).

Therapy will be immediately discontinued for any grade IV treatment-related toxicity that becomes apparent. The exception to this is for grade 4 neutropenia of $<$ 7 days duration. Study treatment will be reinitiated for any grade treatment-related III toxicity pending the reversal of such toxicity after withholding treatment (i.e. the toxicity resolves to the subject's baseline level). In the event of any adverse effect, appropriate medical treatment will be instituted and study treatment will be discontinued if the above toxicity remains.

PROTOCOL TITLE: Phase 2A Study Evaluating a Chemokine-Modulatory Regimen in Patients with Colorectal Cancer Metastatic to the Liver

Table2. Treatment Related Toxicity Management

Treatment-related AEs	Toxicity grade or conditions (CTCAE5.0)	Action taken for Interferon Alpha-2b	Action taken for Rintatolimod	Action taken for Celecoxib	Additional actions
Chills/Fever	Grade 3	None	None	None	Consider additional acetaminophen dosing, supportive care
Pancreatitis	Grade 3	Hold Decreased future doses by 50%	Hold	Hold	Supportive measures as clinically indicated
AST / ALT elevation or Increased bilirubin	Grade 3	Hold until improved to grade 1; Decrease future doses by 50%	Hold	Hold	Advise evaluation for other possible etiologies; consider imaging
Vomiting	Grade 3	Hold until resolved to grade 1; Decrease future doses by 50%	Hold	Hold	
Neuropathy	Grade 2 or greater	Hold until decreased to patient's baseline; Decrease future doses by 50%	None	None	
Depression or other clinically relevant mood disorder	Grade 3	Permanently discontinue; appropriate supportive care/intervention	None	None	
Neutropenia	Grade 3 or greater	Hold until ANC > 1000; Decrease future doses by 50%	Hold	Hold	
Hemorrhage	Grade 2 or greater	None	None	Permanently discontinue	
Myocardial infarction or other arterial thrombotic event	Grade 2 or greater	None	None	Permanently discontinue	

PROTOCOL TITLE: Phase 2A Study Evaluating a Chemokine-Modulatory Regimen in Patients with Colorectal Cancer Metastatic to the Liver

Treatment-related AEs	Toxicity grade or conditions (CTCAE5.0)	Action taken for Interferon Alpha-2b	Action taken for Rintatolimod	Action taken for Celecoxib	Additional actions

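### The suspension list in 19.4 requires 7 events at 13 subjects where the stated rule and Table X require 6, and 10.2.3 and 19.4 name different events for that rule

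*Combined protocol and SAP*

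**What the plan says.** **Threshold.** Section 19.4 (Safety Monitoring) sets a limit of .33 on the proportion of subjects with a treatment-related SAE, a posterior cutoff of .80 and a Beta(1,2) prior. Table X tabulates the resulting counts. Its row for 13 subjects reads 6 events, posterior .805, binomial tail .233, and 7 events first appears at 14 subjects. The text then says "The table above presents the minimum number of subjects experiencing treatment-related SAEs" that would lead to suspension. The list that follows puts 6 events at 11–12 subjects and "7 subjects experience treatment related SAE among 13 – 15 subjects".

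**Counted events.** Section 10.2.3 (Toxicity Management) introduces the rule: "Rather than a separate phase of the study to characterize safety, we will use continual Bayesian monitoring of SAEs with a stopping rule". It continues: "We will focus on monitoring for grade 3 or greater treatment related hematologic toxicities, and grade 4 or greater treatment related non-hematologic toxicities", and refers to 19.4 for details. In 19.4, "Treatment Related SAEs will be defined as the following events" opens a list of three items:
- related non-hematologic toxicity of grade 3 or greater, with exceptions for some toxicities lasting under 7 days;
- an item that reads, at or above this level, "Grade 4 treatment related non-hematologic toxicity";
- Hy's law.

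No hematologic toxicity is listed.

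**The concern.** At 13 subjects the list and the table cannot both be followed. With 6 events the stated rule suspends the trial and the list lets it continue. Planned enrolment is 15, so the trial will reach 13 unless it stops earlier.

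On the events, 10.2.3 relies on this rule instead of a separate safety phase and tells the reader that hematologic toxicity is part of it. Under 19.4, which is the operative text, an isolated non-fatal hematologic toxicity adds nothing to the count. The two sections also differ on non-hematologic toxicity, which starts at grade 4 in 10.2.3 and at grade 3 in 19.4.

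**Working it through.** **Inputs (19.4):** prior Beta(1,2), limit .33, cutoff .80, enrolment 15. With r events in n subjects the posterior is Beta(1+r, 2+n−r).

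**Reproducing Table X.** For whole-number parameters, P(Beta(a,b) > x) = P(Bin(a+b−1, x) ≤ a−1). At n = 13, r = 6 the posterior is Beta(7,9), so the probability is P(Bin(15, .33) ≤ 6) = 1 − P(X ≥ 7 of 15). Table X's own row for 15 subjects prints that tail as .195, and 1 − .195 = .805, the figure printed at 13. All 14 rows reproduce to three decimals on both the posterior and binomial columns, and the table's count is the true minimum at every n from 2 to 15.

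**The row for 13 subjects:**

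| Events in 13 | Posterior P(π > .33) | Stated rule | 19.4 list |
|---|---|---|---|
| 5 | 0.6291 | continue | continue |
| 6 | 0.8049 | suspend | continue |
| 7 | 0.9163 | suspend | suspend |

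The list agrees with the table at every other n.

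**Effect on the chance of suspension by 15 patients** (exact recursion over patients 1 to 15):

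| True rate | First crossing at 13 | By table | By list | Difference |
|---|---|---|---|---|
| 0.20 | 0.0051 | 0.1047 | 0.1015 | 0.003 |
| 0.25 | 0.0123 | 0.1900 | 0.1831 | 0.007 |
| 0.33 | 0.0295 | 0.3815 | 0.3683 | 0.013 |
| 0.40 | 0.0432 | 0.5752 | 0.5596 | 0.016 |
| 0.50 | 0.0460 | 0.8136 | 0.8021 | 0.012 |

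The difference is the chance of first crossing at 13 times the chance of no further event in patients 14 and 15. At 0.40 this is 0.0432 × 0.60² = 0.016.

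**Counted events, side by side:**

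| Related event | 10.2.3 | 19.4 |
|---|---|---|
| Hematologic, grade 3 or greater | counted | not listed |
| Non-hematologic, grade 3 | not counted | counted, with exceptions |
| Non-hematologic, grade 4 or greater | counted | counted |
| Hy's law | not named | counted |

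**Illustration.** Suppose 5 of the first 10 patients have only a related grade 3 hematologic toxicity. If counted, the posterior is P(Beta(6,7) > .33) = 0.829, which suspends. If not counted, it is P(Beta(1,12) > .33) = .67¹² = 0.008, which continues. The documents give no hematologic rate for this schedule. The chance of 5 or more in 10 is 0.002 at an assumed 10%, 0.010 at 15%, and 0.065 at 23.8%, the myelosuppression figure that 10.2.3 cites from a longer interferon schedule.

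**The case against.** On the threshold, the discrepancy affects one sample size late in a small trial. Posterior probability at 6 of 13 sits close to the cutoff: a limit of exactly 1/3 gives 0.7970 instead of 0.8049, and that limit reproduces the list at every n from 2 to 15. The list may therefore be a rounding variant. The rule and the table stand in the same section, suspension is for review and not closure, and one more event at 14 or 15 would trigger the list as well. All of this bears on size. It does not rescue the list, because text and table state .33 and a 1/3 limit does not reproduce the printed posteriors (at 10 subjects it gives .822 where the table prints .829).

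On the events, 10.2.3 speaks only of a focus and defers to 19.4, whose explicit definition governs and is broader for non-hematologic toxicity. A non-hematologic consequence of cytopenia, such as a related grade 3 infection, would count under 19.4. Individual patients are protected:
- ANC must be at least 1000 before each 3-day block (10.1.1).
- All three drugs are held for neutropenia of grade 3 or greater (10.2, dose modification table).
- Therapy stops for related grade 4 toxicity, except grade 4 neutropenia under 7 days (10.2).

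The death trigger, the annual DSMC review (both 19.4) and the EPCT meetings (Section 20) also remain. These points stand, so the omission is not shown to be a safety gap and may be deliberate. The two sections still describe one rule differently.

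**Conclusion.** Both parts hold. The list is wrong at 13 subjects given the stated prior, limit and cutoff. The error is certain and runs in the permissive direction, and it costs 0.3 to 1.6 percentage points of suspension probability at true rates of 0.20 to 0.50, assuming independent patients with a common rate and a check after each one.

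The event conflict is one of wording, with intent unknown and size not estimable from the documents. It concerns what the trial-level rule counts and does not mean that safety oversight is absent. Together they should be fixed: the rule is operative, and the corrections are short.

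**What to change.** 1. In the 19.4 list, write 6 events among 11–13 subjects and 7 among 14–15. This costs one line.
2. Use one event definition in 10.2.3 and 19.4, with the non-hematologic grade in 10.2.3 brought into line with 19.4. For hematologic toxicity there are two routes:
   - **(a)** Add it to 19.4 at a grade and duration set by the sponsor's clinicians, consistent with the 10.2 exemption for grade 4 neutropenia under 7 days. This makes suspension more likely. At an assumed 15% non-hematologic rate and an independent hematologic rate of 5% to 15%, the combined rate is 1 − 0.85 × 0.95 = 19.3% to 1 − 0.85 × 0.85 = 27.8%. The chance of suspension by 15 patients on the Table X boundary rises from 4.9% to between 9.4% and 24.9%.
   - **(b)** Remove the hematologic statement from 10.2.3. This changes wording only and leaves the 19.4 event count as it is, with hematologic toxicity outside the trial-level rule.

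The choice between (a) and (b) is clinical. The statistical requirement is that the two sections agree.
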